Strengthening the South African Health System's Response to HIV through Youth Lay Health Workers:

an Impact Evaluation

Short Title: Impact Evaluation of Project Unlocked [project name changed to Youth Health Africa

in 2020]

Protocol Version: 1.1 (19 October 2019)

Funder: Aurum Unlock'd Joint Venture

Implementing Partners:

The Aurum Institute for Health Research (Aurum), South Africa Aurum Unlock'd Joint Venture [name changed to Youth Health Africa in 2020] The University of Washington

Principal Investigator: [name] (Aurum)

Co-Principal Investigator: [name] (University of Washington)

STUDY SUMMARY

Background: South Africa has the greatest burden of HIV globally, with numerous economic, social, and structural issues perpetuating the epidemic. Placement of disenfranchised youth as temporary lay health workers in health facilities has the potential to mitigate some of the issues that perpetuate the epidemic: shortage of human resources in the health system and youth unemployment. Project Unlocked, a Joint Venture between Aurum and Unlock'd, is training and placing disenfranchised youth as administrative and programmatic interns in health facilities in South Africa, in part to strengthen the health system's HIV response.

Aims: This study will assess whether placing youth as temporary lay health workers in clinics can strengthen the health system's HIV response in South Africa.

Objectives. This study will assess the change in health facilities' HIV program performance due to Project Unlocked. The primary objective is to examine the direct impact of the project by assessing difference in programmatic indicators related to 90-90-90 targets after nine months of implementation.

Methods: We will utilize a prospective, cluster randomized design among 18-24 facilities in Northwest Province to assess the ability of Project Unlocked to strengthen the HIV response South Africa. Facilities will be randomized to either the control arm (to receive administrative interns) or the intervention arm (to receive administrative and programmatic interns) for nine months. We will use routinely collected, programmatic data to evaluate the difference in HIV performance between control and intervention sites during nine months of implementation.

1.1. Background

South Africa has the greatest burden of HIV globally, home to one-in-five people infected with HIV, or approximately 7.7 million people living with HIV (PLHIV) (1). While South Africa has made great strides in addressing the HIV epidemic, much work remains to reduce new infections and reach the level of detection, treatment, and viral suppression necessary to quell the spread of HIV (1,2). In 2018 alone, an estimated 240,000 people were newly infected with HIV in South Africa (1). Furthermore, it is estimated that while 90% of PLHIV know their status, only 62% of these are on treatment and only 54% have reduced viral loads (1)— numbers that fall far short of the 90-90-90 targets that must be met to reverse the HIV epidemic (2). Youth, especially young women, bear a disproportionate burden of HIV (3), and they lag behind other age groups for testing and treatment (4,5).

Numerous underlying economic, social, and structural issues perpetuate the epidemic in South Africa (6). In particular, shortages of human resources have resulted in a significant challenge for the public healthcare system that has impeded the HIV response (7), as insufficient human capacity can hinder quality of and linkage to care (8). Improved clinic operations have been linked to improved care, e.g., uptake of ART (9), but are difficult to undertake with limited human resources. Economic pressures can also drive the HIV epidemic. Disenfranchised youth, i.e., adolescents and young adults with limited access to education and employment, are especially at risk for HIV (10–12). Addressing this issue is imperative to ending HIV in South Africa where over half of people aged 15-24, and 38% of people aged 15-35, are unemployed (13).

These challenges are not unique to South Africa but are rather ubiquitous across Sub-Saharan Africa. Health systems across low and middle-income countries struggle from inadequate human resources (14), and youth unemployment is one of the biggest development challenges for many Sub-Saharan African countries (15,16).

Disenfranchised youth represent a wealth of potential for the understaffed health system in South Africa. Lay healthcare workers, paid or unpaid, have been viewed as a critical piece of strengthening linkage to healthcare in many settings (17). Past research shows that lay health workers can significantly improve linkage to care, but numerous challenges exist in ensuring quality and sustainable lay health worker interventions (18–23). In particular, there is little known on whether placing disenfranchised youth as lay healthcare workers could bolster the health system's HIV response. Research is therefore needed to understand what role, if any, youth can serve as lay healthcare workers to effectively bolster the HIV response in South Africa. The findings of such research could be applicable not just in South Africa, but across the Sub-Saharan region, where countries struggle with similar issues of limited human capacity in the healthcare sector and high youth unemployment.

1.2. Project Unlocked

In South Africa, a joint venture between Aurum Institute and Unlock'd¹, a local youth talent development business, was launched in 2018 to roll-out a novel youth unemployment project designed to increase the employability of disenfranchised youth by training and placing youth in one-year internships at health facilities. (The Joint Venture between Aurum and Unlock'd is henceforth called Project Unlocked in this protocol.) This project has dual goals to (1) improve the employability and livelihoods of the youth it engages, but also (2) strengthen the HIV response in South Africa. Youth are placed in HIV-related programmatic and administrative roles in health clinics; they receive training and mentorship from program leaders as well as a designated supervisor at the facility so they can be successful on the job.

While the youth learn skills that will make them more employable post-internship, the youth are also contributing to the HIV response of the health facility where they are placed. Youth, who are most commonly referred to as "interns" in Project Unlocked, can be placed in a wide number of roles, ranging from

¹More on the Unlock'd organization can be found at http://www.unlockd.co.za/site/index.

administrative (e.g., file clerks) to programmatic (e.g., testing people for HIV or helping people who have tested positive for HIV to navigate care). In many cases, interns fill roles that were previously vacant. In other cases, interns fill new positions that the facility created to bolster programmatic or administrative support to clinic staff. Examples of the roles that youth occupy are outlined below in Figure 1.

[figure not shown]

Figure 1. Overview of the programmatic and administrative roles that interns fill in Project Unlocked, and the potential to impact HIV programs in the health systems where they are placed.

1.3. Problem Statement

While Project Unlocked has scaled up rapidly in its first year of operation, there is a need to conduct a rigorous evaluation of the project to determine its impact on the health system. While many programs use lay health workers for health system strengthening, none to our knowledge specifically rely on identifying and training unemployed youth, specifically youth who are themselves at greater risk of HIV, to fill these roles on a temporary basis. While the Joint Venture has preliminary evidence to suggest that Program Unlocked benefits the interns, evidence is needed to understand the impact the program has on the health system in which it operates.

The proposed study will therefore assess whether placing youth as temporary lay health workers in health facilities can strengthen the health system's HIV response in South Africa. We will utilize a nine-month prospective, cluster randomized design to study the ability of this novel youth employment project to strengthen the HIV response in South Africa as implemented under routine, programmatic settings.

2. AIMS AND OBJECTIVES

2.1. Study aims

This study seeks to determine the impact that temporary youth interns, who serve as lay healthcare workers through Project Unlocked, have on the health system's HIV program performance. Specifically, we aim to understand what impact, if any, Project Unlocked interns have on the ability of the health facilities where they are placed to test people for HIV, initiate newly diagnosed HIV-positive persons on treatment, and retain people with HIV in care, as we hypothesize these are the portions of the program that the interns can directly impact (see Figure 1). That is, interns serving as self-screeners would be expected to impact HIV testing rates, while interns serving as patient navigators would be expected to impact linkage to care, and interns serving as tracers would be expected to impact overall retention in care. There could also be broader effects on the HIV program

(e.g., TB case finding, initiation of TB prophylactic treatment). A controlled study is needed to ascertain what, if any, impact this project has on these indicators.

Assessment of these aims involves analysis of routinely collected facility data (e.g., data Aurum receives to monitor facility performance and report to PEPFAR). **No primary data collection will be required**. Study objectives will be studied through use of routinely collected data, which Aurum routinely uses to monitor clinics (e.g., TIER.Net and DHIS).

2.2. Study objectives

Primary Objective: The primary objective of this study is **to quantify the change** in HIV program performance among health facilities with Project Unlocked interns in programmatic roles (intervention sites) versus health facilities where Project Unlocked interns are not in programmatic roles (control sites) by examining the difference in programmatic indicators related to **90-90-90 targets**.

- **HIV testing (90)**: Percentage of individuals who received HIV testing services (HTS) and received their results, among all persons who were seen at the facility.
- **Linkage to treatment (90-90)**: Percentage of individuals testing positive who were linked to treatment at the facility (same day of testing and by 14 days post-testing).
- **Retention in care (90-90-90):** Percentage of people on treatment for HIV who default from treatment. This measure will be used as a proxy for viral suppression, which is the "third 90" of the 90-90-90 targets.

Analyzing the 90-90-90 targets is the primary objective for this study, as the interns in programmatic roles are performing activities directly linked to these indicators, i.e., testing, linkage to care, and retention in care (see Figure 1). As such, we have reason to believe interns could **directly impact performance**, as measured by these indicators.

Secondary Objective: We will measure how the presence of interns at health facilities **indirectly** impacts other HIV services that are not directly part of the programmatic interns' work responsibilities, such as initiation and completion of isoniazid preventive therapy (IPT) among people newly diagnosed with HIV. The indicators used to measure the secondary objectives will also be those routinely reported (i.e., through DHIS and TIER.Net).

2.3. Hypothesis

We hypothesize that intervention clinics will experience a significant improvement in HIV testing, linkage to care, and retention in care as compared to control clinics, as program interns will directly contribute to improvements in related services. We hypothesize that intervention clinics will also experience improvement in other HIV programmatic areas that are not directly related to the roles and responsibilities the interns hold.

3. METHODS

3.1. Study Design

We propose a nine-month cluster-randomized controlled trial (cRCT) with 18-24 clinics in Northwest Province to quantify the impact of Project Unlocked on HIV testing, treatment, and retention in care. Health facilities, and not individuals within the facilities, will be the unit of analysis. No data from individuals will be collected. All data will be collected at the facility level. Only routinely collected data will be utilized in this study.

3.2. Study Location and Population

HIV facilities: This study will primarily be conducted among health facilities in Ngaka Modiri Molema (NMM) district in Northwest Province, for which Aurum is the PEPFAR implementing partner. We selected NMM district because the majority of facilities in this district have not yet participated in Project Unlocked but have expressed interest in the program. There 31 facilities in NMM district currently eligible for this study. These facilities and accompanying details are described in Table 1 (see next page). Project activities will be expanded to facilities in

other districts in Northwest Province if needed for operational reasons or to maintain the power required for this study.

HIV clinics are actively recruited to participate in Project Unlocked. Aurum uses its position as Implementing Partner to identify clinics where additional capacity for non-clinical HIV activities is necessary, and thus identify clinics that could benefit from the Project Unlocked model.

Youth Interns: Project Unlocked passively recruits youth to participate in this project, relying on flyers at community-level health facilities and word of mouth to encourage application to the program. The target youth population for the project is aged 18-30 with low socioeconomic status, minimal education, and limited job experience. The median age of participation is approximately 25 years; youth under 18 are not part of this project. Youth are selected into the program based on the level of need at the HIV clinics in their communities, not based on the youth's skill set or experience.

Table 1. Facilities in NMM district, Northwest Province eligible for inclusion in proposed cluster RCT. Averages were calculated from October 2018-July 2019.

Facility name	Local Municipality	Avg No. Patients / Month	Avg No. Tested/ Month	Avg No. Newly Positive/ Month	Avg No. Initiated/ month	Avg No. Initiated on same day/ month	Total No. On ART (July 2019)	Total No. Default Early (July 2019)
Agisanang Clinic	anang Clinic Tswaing		264	7	7	4	740	76
Bakerville Clinic	Ditsobotla	1075	72	3	4	1	327	67
Blydeville Clinic	Ditsobotla	1244	116	9	8	4	577	99
Blydeville Old	Ditsobotla	1640	209	12	10	5	719	139
Bodibe 1 Clinic	Ditsobotla	3274	501	14	14	10	1181	225
Boikhutso Clinic	Ditsobotla	3907	669	21	20	10	1577	268
Braklaagte	Ramotshere Moiloa	1661	105	5	5	4	536	72
Coligny CHC	Ditsobotla	3033	426	14	14	2	1013	200
Delareyville CHC	Tswaing	2938	416	23	24	17	1331	335
Dinokana CHC	Ramotshere Moiloa	3593	453	12	14	10	1211	104
Dinokana old	Ramotshere Moiloa	1528	184	6	6	2	702	43
Driefontein	Ramotshere Moiloa	837	85	1	2	1	249	38
Ganalaagte Clinic	Tswaing	2948	244	10	13	6	1254	189
Gopane	Ramotshere Moiloa	1882	226	4	4	0	501	45
Groot Marico	Ramotshere Moiloa	1072	147	6	5	3	494	92
Itekeng Clinic	Ditsobotla	1419	205	4	5	4	526	137
Itsoseng CHC	Ditsobotla	4350	469	13	13	4	1279	191
Itsoseng Clinic	Ditsobotla	1555	105	5	5	2	537	105
Kunana Clinic	Tswaing	1949	141	4	5	0	581	82
Lehurutshe Hospital	Ramotshere Moiloa	1462	184	7	8	1	181	24
Letsopa Clinic	Tswaing	2885	447	12	14	7	966	124
Mokgola	Ramotshere Moiloa	1611	159	4	5	3	486	57
Motswedi	Ramotshere Moiloa	1344	221	5	5	3	485	44
Ntsweletsoku	Ramotshere Moiloa	1034	20	3	6	1	425	86
Ottosdal CHC	Tswaing	2892	255	10	9	4	828	335
Rietpan	Ramotshere Moiloa	750	134	3	4	2	243	18
Sannieshof CHC	Tswaing	1550	97	7	6	3	449	59
Tlhabologang Clinic	Ditsobotla	2475	289	9	9	4	680	211
Tswelelopele CHC	Ramotshere Moiloa	2698	394	13	12	7	1040	98
Vriesgewacht Clinic	Tswaing	1598	145	4	5	3	447	79
Zeerust	Ramotshere Moiloa	1272	271	14	11	10	736	56

3.3. Study arms

There will be an equal number of facilities in the control and intervention arms (1:1 randomization). Facilities are the unit of analysis and will be randomized to the control or intervention arms. Each participating facility will receive a similar number and allocation of youth interns at the facility for a year.

Control arm: Facilities in the control arm will receive the minimum package for the intervention at baseline, i.e., 1-2 interns who will be assigned to administrative roles, such as admin clerk, file clerk, or data capturer.

Intervention arm: Facilities in the intervention arm will receive the minimum package and the intervention package at baseline. That is, they will receive 1-2 interns placed in administrative roles (admin clerk, file clerk, or data capturer) and 2-3 interns placed in programmatic roles according to the needs of the facility, one of each of the following: self-screener, patient navigator, and/or tracer. The number of interns allocated to the clinic will be based on the size of the clinic; whether the clinic receives two or three program interns, they will cover self-screening, patient navigating, and tracing. Interns engaged in self-screening will provide pre-counselling to patients and support the patient's use of the self-screening kit. The intern will provide a post-counselling session if the patient tests negative or connect them with one of the facility's lay counsellors if the test is positive. (Note: The self-screening test is used only as a screening test and requires confirmation using traditional testing methods if positive, per South Africa's current national protocol.) Interns placed as patient navigators and tracing will support roles as outlined in Figure 1 (see page 2).

We will aim for control and intervention sites will be similar in all essential regards, other than receipt of the intervention package, as all facilities come from a similar geographic region (i.e., NMM district, Northwest province, South Africa) and are similarly managed (i.e., Aurum is the implementing PEPFAR partner for HIV work at each facility). While differences between facilities do exist, randomization of facilities to the control or intervention arms will result in balanced differences between arms and minimize bias. Preliminary data collection at clinics will be done prior to randomization and restriction may be applied based on those results.

3.4. Randomization of study clinics

All facilities that are eligible and willing to participate in this study (18-24 facilities) will be randomized to the control or intervention arm. We will use stratification improve similarity between facilities in the treatment and control groups. Facilities will be, at minimum, stratified by HIV programmatic performance (measured by HIV testing) and, if necessary, also stratified by size (measured by total monthly head count at the facility). The final decisions for stratification will be driven by the facility data observed in the year proceeding the study. The minimal proposed stratification is outlined in Figure 2.

We will randomize an equal number of facilities to the control or intervention group within each strata using a random number generator. We will randomly assign facilities at a joint meeting between study implementors and program staff (e.g., the NMM health district manager).

[figure not shown]

Figure 2. Allocation of facilities to control or intervention

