7. STATISTICAL CONSIDERATIONS

7.1. Sample size estimation

Sample size: We will enroll 18-24 clinics in this study, resulting in 9-12 clinics being in the treatment and the control arms of the study. The sample size is pre-determined by the number of available eligible clinics.

Study power: In Table 4 below, we show the minimum detectable differences in HIV testing that can be detected with 80% power under different assumptions of the intra class correlation (ICC) (0.01-0.05), at 5% level of significance, and for different cluster size (number of facilities). For example, if there are 24 facilities in this study (12 in each of the study arms), we will have 80% power to detect a difference of at least 35% in HIV testing when the ICC is 0.01, and at 5% level of significance. Similarly, if we have 18 facilities in this study (9 in each of the study arms), we will have 80% power to detect a difference in HIV testing of at least 45% when the ICC is 0.01, and at 5% level of significance.

These power calculations are based on data on the eligible facilities from the NMM district that show there was an average of 1,687 people tested for HIV in six months per clinic and that average HIV testing was at 14% in this time period.

Significance level	Power	Current proportion of total headcount tested for HIV	Number of clusters	Average cluster size	Coefficient of variation (cv)	ICC	Proportion of headcount tested for HIV needed to achieve 80% power
5% 80%						0.01	0.19
	0.14	12	1687	0.596	0.03	0.23	
						0.05	0.26
5%	80%	0.14	9	1687	0.596	0.01	0.20
						0.03	0.25
						0.05	0.28

Table 4. Assumptions for power calculations, with estimated HIV testing level needed to achieve 80% power.

Statistical analyses

The first three months of the study comprise the "run in" period. Data from the wash-out period will not be used in the analysis. We will use six months of facility data collected during months 4-9 of the intervention for this analysis.

We will employ 'Cluster-level' methods to conduct statistical analysis in a two-stage approach here. The first step will consist of estimating a summary measure for each cluster (facility): we will calculate the % tested for

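### The protocol commits to balancing only HIV testing, one of three primary outcomes, so its flat statement that randomisation will balance 9-12 facilities per arm is not supported for linkage and retention

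*Protocol*

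**What the plan says.** The allocation is 1:1: "There will be an equal number of facilities in the control and intervention arms (1:1 randomization". Section 3.4 states that "All facilities that are eligible and willing to participate in this study (18-24 facilities) will be randomized to the control or intervention arm", and Section 7.1 gives the size of each arm: "resulting in 9-12 clinics being in the treatment and the control arms of the study".

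On balance, the protocol has one firm commitment and three open provisions:

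- **Firm (Section 3.4):** "Facilities will be, at minimum, stratified by HIV programmatic performance (measured by HIV testing".
- **Conditional (Section 3.4):** facilities are, "if necessary, also stratified by size (measured by total monthly head count at the facility".
- **Deferred (Section 3.4):** "The final decisions for stratification will be driven by the facility data observed in the year proceeding the study".
- **Optional (Section 3.3):** "Preliminary data collection at clinics will be done prior to randomization and restriction may be applied based on those results". No variable, criterion or trigger is given.

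Section 3.3 also asserts that "randomization of facilities to the control or intervention arms will result in balanced differences between arms and minimize bias".

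Section 5.1 ranks testing, linkage and retention together as three primary outcomes. Under the statistical analyses heading in Section 7, each is compared with a weighted two-sample t-test on facility summaries. Adjustment for facility-level factors appears only as an additional analysis where needed, and no factor is named. Section 8 lists the small number of clinics as a limitation but does not mention imbalance between arms.

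**The concern.** Stratifying on one outcome balances another only as far as the two are related. If testing is a poor guide to linkage and default, the one committed stratifier leaves two of the three primary outcomes to simple chance, with 9-12 units per arm. The main comparison is unadjusted, so a baseline gap that persists into months 4-9 would carry into the estimated effect. A reader of an unblinded trial of this size would find it hard to tell such a gap from an intern effect. Table 1 already holds baseline same-day initiation and early default for the listed facilities, so the information needed to limit this is at hand before the draw.

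**Working it through.** The protocol prints no figure for balance, so there is none to reproduce. Its Table 4 concerns power for testing only.

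**Inputs.** Table 1 of the protocol: head count, number tested, newly positive, initiated same day, total on ART and early default, for 31 facilities. One head count cannot be read in the text at hand, so 30 facilities are used wherever the testing rate is needed. Facilities randomised: 18 or 24 (Section 3.4), 1:1 (Section 3.3).

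**Step 1: baseline values per facility.**
- % tested = tested / head count
- Same-day linkage = initiated same day / newly positive
- Early default = default early / total on ART

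Same-day linkage has mean 51%, SD about 25 points and range 0-100%. Early default has mean 16.2%, SD 7.4 points and range 6.1% (43/702) to 40.5% (335/828). Half an SD is therefore about 0.5 × 25 = 12.5 points for linkage and 0.5 × 7.4 = 3.7 points for default.

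**Step 2: how far testing predicts the others.** Pearson r between % tested and same-day linkage is 0.25, so r² = 0.06. Between % tested and early default r is -0.26, so r² = 0.07. Head count does no better (Spearman -0.07 and 0.09).

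**Step 3: analytic check, no stratification.** The standard error of a standardised arm difference is √(2/n), with n facilities per arm.
- n = 9: √(2/9) = 0.471; P(|d| > 0.5) = 2 × [1 - Φ(0.5/0.471)] = 0.29
- n = 12: √(2/12) = 0.408; P(|d| > 0.5) = 2 × [1 - Φ(0.5/0.408)] = 0.22

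Treating linkage and default as independent, the chance that at least one exceeds 0.5 SD is 1 - 0.71² = 0.50 and 1 - 0.78² = 0.39.

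**Step 4: simulated allocation.** Draw 18 or 24 facilities from Table 1, stratify, split 1:1 within strata, and record the baseline arm differences (10,000 runs per scheme). The chance that linkage or default differs by more than 0.5 SD is:

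| Scheme | 18 facilities | 24 facilities |
|---|---|---|
| No stratification | 52% | 42% |
| Two testing strata | 51% | 41% |
| Three testing strata | 52% | 40% |
| Two testing × two size strata | 53% | 42% |

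Differences of a point or so are simulation error. With two testing strata the median gap is 8.5 points (18) or 7.3 points (24) for linkage, and 2.4 or 2.1 points for default. Stratification does work for testing itself: the chance of a gap over 0.5 SD falls from 29% to 8% (18) and from 23% to 4% (24).

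**Step 5: effect of restriction.** Keep the testing strata and draw only from the best-balanced 10% of allocations on testing, same-day linkage and early default. The 90th percentile of the baseline gap then changes as follows:

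| | 18 facilities | 24 facilities |
|---|---|---|
| Same-day linkage, points | 19.7 to 5.9 | 17.8 to 5.3 |
| Early default, points | 5.7 to 1.8 | 4.9 to 1.5 |

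The chance of a gap over 0.5 SD in either falls to about 0%.

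**The case against.** A reader might infer that the trial is balanced on testing alone and that a large imbalance is likely. The protocol does not support either reading.

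- **Wider balancing is permitted.** Testing is stated as a minimum, the final strata await pre-study data, and restriction is expressly allowed. The details could sit in a randomisation procedure or analysis plan not shown here. This stands: the gap is in what is committed to.
- **How likely depends on the cut-off.** Counting a gap over 10 points in linkage or 3 points in default gives 57% (24 facilities) or 66% (18). Those cut-offs lie about one SD of the arm difference from zero (SDs of about 10.5 and 3.0 points with 24 facilities), and two independent normal differences would exceed such limits about 55% of the time in any trial. Doubling the cut-offs gives 10% and 18%. At 0.5 SD the odds are roughly even or somewhat lower.
- **Chance imbalance is not bias.** Randomisation balances in expectation, and the t-test's standard error allows for chance differences. Adjusted analyses are also planned, though as additional ones.
- **The baseline data are imperfect.** Same-day linkage comes from small rounded monthly counts: 12 of the 30 facilities have five or fewer new positives a month. Among the 21 with at least five, its SD is 19 points, not 25. Without the one extreme facility, the default SD is 6.0 points. Table 1 has no 14-day linkage or late default, and Section 3.2 allows facilities from other districts.
- **The near-0% after restriction is almost built in,** because allocations are scored on the variables used to select them. It shows baseline balance. The gain at months 4-9 depends on how well baseline predicts outcome, which the protocol does not give.

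Stratified 1:1 allocation remains a valid design. What these points leave untouched is that the committed stratifier, and the optional size strata, do almost nothing for linkage and default, while Section 3.3 promises balance without qualification.

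**Conclusion.** The point holds in a limited form. The protocol firmly commits to balancing one of three primary outcomes. By its own Table 1, that gives the other two essentially no more protection than unstratified allocation: a 41% (24 facilities) to 51% (18) chance of a baseline gap over 0.5 SD in at least one. The promise of balance in Section 3.3 is therefore too strong for 9-12 facilities per arm. The cost is lost precision and credibility. Neither a biased test nor an inflated type I error follows.

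The figures assume two testing strata (Figure 2 is not shown; three strata or added size strata change little), 0.5 SD as the mark of a material gap, enrolled facilities resembling those in Table 1, and October 2018-July 2019 values standing in for the outcomes. This is a cheap improvement that should be made; the design is not invalid without it.

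**What to change.** 1. **Randomisation (Sections 3.3 and 3.4).** Replace the optional restriction with a commitment to covariate-constrained randomisation on baseline % tested, same-day linkage, % early default and head count. Use the pre-randomisation data of the facilities actually enrolled, and add 14-day linkage and late default if the routine reports supply them. Preset the balance criterion (for example, the best-balanced 10% of allocations), check that no pair of facilities is always together or always apart, and draw one acceptable allocation at random at the public meeting.
2. **Analysis (Section 7).** In the primary analysis of each outcome, adjust for that outcome's own baseline facility value and reflect the restriction in the inference. Keep covariates few: an unadjusted two-sample comparison has 18 - 2 = 16 to 24 - 2 = 22 degrees of freedom, and one covariate leaves 15 to 21.
3. **Wording (Section 3.3).** State that randomisation balances the arms in expectation and that restriction limits chance imbalance.

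The cost is a short program run before the draw on data that are routinely reported, a draw slightly harder to explain in public, and one degree of freedom per covariate. If the draw has already been made, only items 2 and 3 remain open, and the inference in item 2 should then reflect the allocation scheme actually used.
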